3.2.11 Summary of Outcome Variables and Analysis Sets

The analysis sets for each outcome variable are provided in [Table 1](#). For some outcome variables, the analysis set will use a further subset (e.g., patients who are evaluable for the analysis of duration of response (DOR) are those who responded in the ORR analysis) which are described in detail in the endpoint analysis sections in [Section 4.2](#).

Table 1 Summary of Outcome Variables and Analysis Sets

Outcome variable	Analysis set
Efficacy data	
ORR by the end of Cycle 16 (primary endpoint)	FAS
Change from baseline in PAINS-pNF chronic target PN pain intensity score at Cycle 12 (1 st key secondary endpoint)	Pain FAS
Change from baseline in PlexiQoL total score at Cycle 12 (2 nd key secondary endpoint)	FAS and Pain FAS (supplementary)
Chronic target PN pain palliation, time to chronic target PN pain palliation	Pain FAS
ORR (single arm), DOR (single arm), PFS (single arm), time to progression (single arm), time to response (single arm), and BOR (single arm)	Selumetinib FAS, Extended Selumetinib FAS, and FAS (selumetinib arm only)
PFS during the randomised period (exploratory endpoint)	FAS
Best percentage change from baseline in target PN volume during the randomised period	FAS
Pain medication, PII-pNF pain interference total score, PROMIS Physical Function items, Peds QL Inventory (NF1 Module Acute Version 3.0 – Adult Report), Skin Sensations Domain, EQ-5D-5L, EQ-VAS, PAINS-pNF spike target PN pain intensity score	FAS

Table 1 Summary of Outcome Variables and Analysis Sets

Outcome variable	Analysis set
Percentage change from baseline in target PN volume at Cycle 30 or later.	Fed FAS
Study Population/Demography Data	
Demography characteristics (e.g., age, sex, etc.)	FAS
Baseline and disease characteristics	FAS
Important deviations	FAS
Medical/surgical history	FAS
Previous anti-PN therapy	FAS
Concomitant medications/procedures	FAS
Subsequent anti-PN therapy	FAS
PK Data	
Selumetinib and N-desmethyl selumetinib plasma concentration data and PK parameters	PK
Safety data	
Exposure	Randomised period SAF and On-selumetinib SAF
Adverse events	Randomised period SAF and On-selumetinib SAF
Laboratory measurements	Randomised period SAF and On-selumetinib SAF
Vital signs	Randomised period SAF and On-selumetinib SAF
ECGs	Randomised period SAF and On-selumetinib SAF
Ophthalmologic assessment	Randomised period SAF and On-selumetinib SAF
Physical Examinations	Randomised period SAF and On-selumetinib SAF

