4.2.2.5 Primary Analysis of the 2nd Key Secondary Endpoint

The difference in the mean change from baseline in PlexiQoL total score at Cycle 12 between treatment groups (selumetinib minus placebo), standard error, 95% CI, and p-value will be assessed by LS means of an MMRM with randomised study intervention, cycle number, geographical region and average baseline chronic target PN pain intensity group as categorical fixed effects; the baseline PlexiQoL total score as a continuous covariate; and treatment-by-cycle number and baseline PlexiQoL total score-by-cycle number interactions. Parameters will be estimated with the REML approach, and the Kenward-Roger approximation is used to estimate the degrees of freedom.

The analysis will be performed on a subset of the FAS population with an evaluable baseline assessment and at least one evaluable post-baseline assessment. Evaluable assessment is defined as a PlexiQOL total score. Data collected during the randomised period (see Section 3.3.2.2) will be included, adhering to the intercurrent event strategy (refer to Section 4.2.2.2.3).

The analysis will be conducted using PROC MIXED in SAS using the same model specifications as specified for the 1st key secondary endpoint (see Section 4.2.2.1.5). All main effects and the interaction terms will remain in the model, regardless of significance.

In addition to the Cycle 12 estimate, the model will present LS mean estimates for each treatment group and their differences, standard errors, 95% CIs, and p-values (where applicable and with statistical significance effects being interpreted as nominally significant) for mean changes from baseline to each cycle during the randomised period (based on the treatment-by-cycle interaction coefficient) and the average over the randomised period (based on the treatment coefficient). A plot of the LS means accompanied by the 95% CI will be produced.

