7.5 TFLs for Japan Subpopulation

Details of the specific analyses to be performed for the Japan subpopulation are presented in [Table 18](#).

Table 18 TFLs for Japan subpopulation

Type	Title	Additional Notes
Table	Subject disposition (Japanese)	
 Japan-only enrolled patients
Table	Demographic characteristics (Japanese)	
 Japan-only FAS
Table	Subject characteristics (Japanese) ^a	
 Japan-only FAS
Table	Disease characteristics at baseline (Japanese)	
 Japan-only FAS
Table	Objective response rate by end of Cycle 16, primary analysis, on-treatment MRI volumetric assessments period (Japanese)	
 Japan-only FAS p-value not to be displayed
Table	Target PN volume, actual value and change from baseline (Japanese)	
 Japan-only FAS
Table	PAINS-pNF chronic target PN pain intensity scores: actual value and change from Baseline (Japanese)	
 Japan-only pain FAS
Table	PlexiQoL total scores over time: actual value and change from Baseline (Japanese)	
 FAS
Table	Summary of plasma concentrations (ng/mL) of selumetinib - Multiple dose Cycle 1, Day 8 (Japanese)	
 PK analysis set – Japan subpopulation
Table	Summary of plasma concentrations (ng/mL) of selumetinib - Multiple dose Cycle 1, Day 8 (non-Japanese)	
 PK analysis set - non-Japan subpopulation
Table	Summary of plasma concentrations (ng/mL) of N-desmethyl selumetinib - Multiple dose Cycle 1, Day 8 (Japanese)	
 PK analysis set – Japan subpopulation
Table	Summary of plasma concentrations (ng/mL) of N-desmethyl selumetinib - Multiple dose Cycle 1, Day 8 (non-Japanese)	
 PK analysis set - non-Japan subpopulation
Figure	Combined individual plasma concentrations (ng/mL) of selumetinib versus time - Multiple dose Cycle 1, Day 8 (linear scale) (Japanese vs non-Japanese)	
 PK analysis set - Japan and non-Japan subjects to be displayed on the same plot using different colours for each subpopulation

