8.2 Analysis Sets

Unless otherwise specified, the definition of the analysis sets will be the same as the global study, as defined in the study main SAP Section 3.2 with only patients from China subpopulation.

Analysis sets for China subpopulation analysis include the following:

- China-only enrolled subjects
- China-only full analysis set (FAS)
- China-only pain FAS
- China-only selumetinib FAS
- China-only extended selumetinib FAS
- China-only randomised period safety analysis set (SAF)
- China-only on-selumetinib SAF
- Pharmacokinetic (PK) analysis set (Chinese sub-population vs non-Chinese subpopulation)

The analysis sets used for each outcome will also be the same as defined in the study main SAP Section 3.2.11.

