Figure	LS mean change from baseline in PAINS-pNF chronic target PN pain intensity score over the randomised period (Chinese)	China-only pain FAS
Table	PlexiQoL total scores over time: actual value and change from Baseline (Chinese)	China-only FAS
Figure	Mean change from baseline for PlexiQoL total scores (Chinese)	China-only FAS
Table	Mean change from baseline for PlexiQoL total score over the randomised period: Primary analysis (Chinese)	China-only pain FAS
Figure	LS mean change from baseline in PlexiQoL total scores over the randomised period (Chinese)	China-only FAS
Table	Objective response rate - single arm, primary analysis, on-treatment MRI volumetric assessments period (Chinese)	China-only selumetinib FAS
Table	Objective response rate - single arm, primary analysis, using non-scaled partial volumes after the second data cut-off, on-treatment MRI volumetric assessments period (Chinese)	China-only selumetinib FAS
Table	Best objective response - single arm, on-treatment MRI volumetric assessments period (Chinese)	China-only selumetinib FAS
Figure	Duration of response, Kaplan-Meier plot, primary analysis, on-treatment MRI volumetric assessments period (Chinese)	China-only selumetinib FAS
Table	Duration of response, primary analysis, on-treatment MRI volumetric assessments period (Chinese)	China-only selumetinib FAS

Table 19 TFLs for China subpopulation

Figure	Duration of response, swimmer plot, primary analysis, on-treatment MRI volumetric assessments period (Chinese)	China-only selumetinib FAS
Figure	Progression free survival, Kaplan-Meier plot, primary analysis, on-treatment MRI volumetric assessments period (Chinese)	China-only selumetinib FAS
Table	Progression free survival, primary analysis, on-treatment MRI volumetric assessments period (Chinese)	China-only selumetinib FAS
Figure	Time to progression, Kaplan-Meier plot, primary analysis, on-treatment MRI volumetric assessments period (Chinese)	China-only selumetinib FAS
Table	Time to progression, primary analysis, on-treatment MRI volumetric assessments period (Chinese)	China-only selumetinib FAS
Table	Time to response, descriptive statistics, primary analysis, on-treatment MRI volumetric assessments period (Chinese)	China-only selumetinib FAS
Table	Best percentage change from baseline in target PN volume, primary analysis, on-treatment MRI volumetric assessments period, randomised period (Chinese)	China-only FAS

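### SAP Table 19 lists the China PlexiQoL primary-analysis table under the China-only pain FAS, which contradicts SAP 8.2, Table 1 and the LS-mean figure listed next to it

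*SAP*

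**What the plan says.** Table 19 in SAP 8.5 sets out the outputs for the China subpopulation and the analysis set for each. It has four PlexiQoL score outputs:

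- a descriptive table, "PlexiQoL total scores over time: actual value and change from Baseline (Chinese", on the China-only FAS;
- a figure of mean change, on the China-only FAS;
- the model-based table, "Mean change from baseline for PlexiQoL total score over the randomised period: Primary analysis (Chinese", on the "China-only pain FAS";
- the LS-mean figure, "LS mean change from baseline in PlexiQoL total scores over the randomised period (Chinese", on the China-only FAS.

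The rest of the SAP is consistent about the set for this endpoint. Section 4.2.2.2.5 (its heading is printed as 4.2.2.5) says of the primary analysis: "The analysis will be performed on a subset of the FAS population with an evaluable baseline assessment and at least one evaluable post-baseline assessment". Table 1 in Section 3.2.11 gives the sets for PlexiQoL as "FAS and Pain FAS (supplementary"). For China, Section 8.2 states: "The analysis sets used for each outcome will also be the same as defined in the study main SAP", and points to Section 3.2.11. Section 8.4 carries over the methods of main SAP Section 4 and lists the China departures. A different analysis set for PlexiQoL is not one of them.

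**The concern.** Section 8.1 gives the purpose of the appendix: to judge whether efficacy and safety in Chinese patients are consistent with the global data, in support of registration in China. The results go into a supplementary CSR. PlexiQoL is the second key secondary endpoint, and SAP 3.3.7 includes it among those intended for label claims.

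A table labelled as the primary analysis should estimate the same quantity as its global counterpart, restricted to one country. On the listed set it would estimate the effect only in participants with baseline pain of 3 or more. A difference between that number and the global one could reflect pain severity at entry rather than region. Under Section 8.4 the table would also carry the number of the global primary table with a country suffix, so a reader would have little reason to suspect a different population.

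**Working it through.** The point rests on comparing entries. Arithmetic serves only to show how far the two sets differ.

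**1. Set for the PlexiQoL primary analysis, by source**

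- Protocol 9.4.2.2.2: FAS participants with a baseline and at least one post-baseline total score.
- SAP 4.2 endpoint table and SAP 4.2.2.2.5: the same evaluable FAS subset.
- SAP Table 1: FAS, with Pain FAS as supplementary.
- SAP 8.2: for China, as in Section 3.2.11, hence China-only FAS.
- SAP Table 19, LS-mean figure: China-only FAS.
- SAP Table 19, primary-analysis table: China-only pain FAS.

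Only the last entry differs.

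**2. Could the row be the planned supplementary analysis?** Two things count against it. The row is labelled as the primary analysis, and no FAS version of the table is listed. Where Table 19 wants an output on both sets it uses two rows, as for eDiary entries on pain medication and for change from baseline in chronic pain medication. The similarly worded PAINS-pNF primary-analysis row is correctly on the pain FAS, so a carry-over from that row is plausible, although the documents do not say so.

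**3. Does the model fit the listed set?** The global PlexiQoL model in 4.2.2.2.5 includes baseline pain group as a factor. Section 8.4 allows a supporting adjusted analysis for China with the same adjustment strategy. By the definition in SAP 3.2.3, everyone in the pain FAS has a baseline score of at least 3. A pain-group factor built on that score has one level there and cannot be estimated.

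**4. How different are the sets?** The inputs are the planned global caps in SAP 3.4: about 106 randomised with a score of 3 or more, and about 40 with a score below 3.

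- Total: 106 + 40 = 146.
- Pain FAS share: 106/146 = 72.6%.
- Share left out: 40/146 = 27.4%, about 27%.

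These are study-wide planning numbers. The documents give neither the number of Chinese participants nor their pain split. The share missing from the China table but present in its figure equals the China share with pain below 3, whatever that proves to be. Stratifying by pain and region balances the arms within strata but does not fix the pain mix within a region, so 27% is a reference value and not an estimate for China.

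**The case against.** The best reply is that the SAP already contains the right answer. Section 8.2 fixes the set by reference to Section 3.2.11, and Section 8.4 announces no change. A careful programmer might query the row, and it is probably clerical. That stands, and it is why this is an internal inconsistency rather than a questionable choice of analysis. It does not remove the problem: Section 8.5 presents Table 19 as the detailed specification of the China analyses, and nothing says which text governs when the two disagree.

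A reader might infer that the whole China consistency check compares different populations. The documents do not support that. The descriptive table, the mean-change figure and the LS-mean figure for PlexiQoL are all on the China-only FAS, so a FAS-based comparison remains. Section 8.4 also makes the China analyses non-inferential, with nominal p-values and no multiple testing procedure.

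It can also be said that the table and the LS-mean figure are not certain to come from one model. Section 8.4 makes the unadjusted analysis primary for China and the adjusted one optional, and Table 19 does not say which feeds each output. That is fair. In the main SAP the LS-mean plot accompanies the primary model, so a match is the natural reading, but the China text does not state it. For the same reason, correcting the set aligns the populations without making the China method identical to the global one.

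Finally, a reader might see the same error in Table 18, where the Japan row "PlexiQoL total scores over time: actual value and change from Baseline (Japanese") is assigned simply to FAS. It is not the same error. The type of set is right and only the Japan-only prefix is missing. Section 7.2 limits every Japan set to patients enrolled in Japan, and the row title is marked as Japanese.

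**Conclusion.** Wrong as written, and minor. One entry in Table 19 contradicts the rule in Section 8.2, the set in Table 1, the primary analysis in 4.2.2.2.5 and the neighbouring figure. Programmed as listed, the only tabulated model-based China estimate for the second key secondary endpoint would apply to participants with baseline pain of 3 or more. It would not be like-for-like with the global FAS estimate or with the China LS-mean figure.

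The size in China is unknown. The planned global share left out is 27%, and it should not be quoted as a share of Chinese participants. The conclusion assumes that the programmer follows Table 19 rather than Section 8.2. The global analysis, its conclusions and its type I error are untouched.

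**What to change.** In SAP Table 19, change the analysis set for the PlexiQoL primary-analysis table to China-only FAS, restricted to participants with a baseline and at least one post-baseline total score. If a pain FAS version is wanted, list it as a separate row labelled supplementary, in line with Table 1.

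The cost is one cell edit before the China outputs are programmed, plus one extra row if the supplementary table is kept. No new data or method is needed.
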